Dental staff also take note about how many times the prisoner ask questions about their findings from the oral examination. If the intervention raises their awareness to oral health, it is likely that those in the intervention group ask more questions during the follow-up period. Hence, this is also a secondary variable of interest.

We choose not to include questions about what sort of criminal offence the prisoner had committed and related questions that could challenge dental staffs perceived safety. For example, knowing you are talking to a sexual offender or murderer is likely to affect our dental staff negatively. When the prisoner signs the consent to participate in the study, he also approves that we are allowed to collect such data from the Norwegian Correctional Service. However, we are still not sure whether they will gain us access to such administrative data.

Randomization:

Randomization is done using the randomization tool www.randomizer.org. We randomize prisoners in the order that we receive lists of prisoners who have signed up to participate. Although this order

may not be random, the randomization process ensures that assignment to treatment and control group is. We block on prison level, to ensure a balance between treatment and control group in each prison. To ensure that there is not, by chance, an unequal assignment into treatment or control, we force the randomization to balance assignment into treatment and control for every fourth prisoner. That is, in groups of four, if the first two are assigned to the treatment group, the next two will be control group. To reduce the likelihood that dental staff in prison could guess the assignment of the next prisoner, we used every fourth prisoner rather than every second prisoner. The order that the prisoners meet may not be the same order as we randomize, further ensuring that dental staff may not guess whether the next prisoner is in the treatment group or not.

It would be very interesting to stratify the sample on gender, however we expect at most only to have a few observations on female prisoners. From early 2022, female prisoners will serve time outside of Rogaland County.

The unit of observation is at individual level. To ensure privacy of the prisoners, we do not collect any information that directly identifies them. However, given the detailed questionnaire, we do collect data that contains identifiable information.

Blinding:

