Prisoners are not informed whether they are in the treatment or control group and are therefore blind to treatment status. Dental staff are blind to prisoners' treatment status at the time of the first oral examination and questionnaire. The prisoner's treatment status is revealed just after this. Hence, dental staff collects all data prior to knowing the prisoner's treatment status, and only learn this when they start the MI-based conversation. When prisoners are back at T1 and T2 for follow-up oral examinations and questionnaires, dental staff might still remember whether the prisoner was treated or not. To partially account for potential bias in the oral examination (assessment of oral hygiene and inflammation in gingival), there are two independent assessments of this at T1 and T2. See pre-specification of analytical decisions for more on this.

Power calculations:

We have used GPower and Optimal Design to conduct power calculations.

GPower is used to calculate required sample size for simple comparison of means for the main variables of interest between the treatment and control group, without considering that data is collected at multiple sites. We choose the non-parametric Wilcoxon-Mann-Whitney test, set alpha to 0.05 and required power to 0.8. There is uncertainty concerning the effect size. Previous literature offers some guidance, however there are several important differences to our study. MI-interventions to change oral health have previously been tested on periodontist patients and patients with mental illness, populations that differ from ours. For our main variable of interest, level of plaque, these studies have found effect sizes ranging from 0.286 to 1.213¹. However, one should note that these studies have used different indexes to measure plaque, questioning the comparability of the effect sizes. Setting the power estimate to a moderate level in this range, to 0.5,

¹ An effect size of 0.286 was found after 12 weeks in Brand et al. (2012), whereas an effect size of 1.213 was found in Godard et al. (2011).

our required sample size is 106 prisoners. If we use a more conservative estimate and set it to the lowest effect size observed in the studies referred to above (0.286), the required sample size is 320.

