Optimal Design is used to calculate the Minimum Detectable Effect Size (MDES) given that we block on prison level. Here we choose the Multi-Site trials under Person Randomized Trials. We set alpha to 0.05 and required power to 0.8. As we block on prison, we set number of sites (J) to 4. There are great uncertainty concerning effect size variation, how much of the variation in the outcome that can be explained by the blocking variable, and how much of the variation in the outcome can be explained by the covariate variable. Thus, we present power calculations based on bounds of these values. We set the range of effect size variation from 0.0 (equivalent to the fixed-effects model) to 0.05. Furthermore, we assume that the blocking variable can explain 20% to 30% of the variation in the outcome. And finally, we use the pre-intervention MPS index score from the oral examination as a covariate, expected to explain 50% to 60% of the variation in the post-intervention MPS index score.

Given these boundaries, and assuming we can recruit 100 prisoners in each prison, the most optimistic scenario allows us to detect an effect size of about 0.15. On the other hand, should we end up in the other end of the boundaries, we are only able to detect an effect size of about 0.55. The calculation is very sensitive to changes in the effect size variation, and less sensitive to changes in how much variation the blocking variable and the covariate variable can explain. The number of prisoners recruited in each prison is also an uncertain number. The prisons differ in size and number of prisoners. We are likely to have more than 100 prisoners recruited in three out of four prisons. The smallest prison in the region has only 18 rooms. The calculations above have not considered the imbalance of prison size.

Pre-specification of analytical decisions

Statistical model specification:

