To test the overall effects of the intervention on our primary and secondary outcome variables, we will conduct non-parametric Wilcoxon Mann-Whitney U-tests. Given the ordinal outcome variables, we consider this test as more appropriate alternative relative to traditional two independent sample t-tests. We will compare the means of the treatment group and the control group at T0, T1 and T2. At T0 we expect no differences in means as no intervention has occurred. At T1 and T2 we expect better scores for the treatment group relative to the control group. Notably, our primary interest will be the difference in means at T1, as we expect more missing data at T2 due to prisoners being released from prison. However, for the intervention to have a long-lasting improvement on the prisoner's oral health, it is important that the intervention successfully enables the prisoner to make lasting changes. If we do not find a statistical difference between the treatment and the control group at T2, however, it may be hard to tell whether this is due to the intervention effect fading out or lack of power. See power analysis for more details on this, in which we show effect sizes possible to detect at different number of observations, given that power is set to 0.8 and number of sites is set to 4. As drop-out increases at T2, the higher the effect size must be for us to be able to detect any statistical difference between the groups.

Moreover, we are going to run multiple ordinal logistic regressions where we include selected covariates (see below). Running regressions allow us to control for the baseline measures of plaque

by using the baseline score of the outcome variables as a lagged dependent variable, in addition to including other covariates likely to correlate with the treatment and to explain variation in the dependent variable. For robustness purposes we also run regressions with fixed effects, controlling for unobserved individual time-invariant characteristics.

Covariates:

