The main covariate included in the analysis is the pre-intervention MPS index score. For our secondary outcome variables, the equivalent pre-treatment observation is used as covariate to control for pre-intervention status. We include these as they are likely to explain a lot of the variation in the outcome variable. Furthermore, we include a dummy variable for each prison, to control for prison-specific variation, and a dummy variable for the person who completed the MI-intervention with the prisoner.

As described below, we will also conduct heterogeneous analysis. Covariates that are relevant for such analysis (HASI and depressive symptoms) will also be included in the overall analysis.

Other covariates may be included, however given that we have successfully randomized prisoners, they should not affect our results. For robustness purposes, we will run analysis that include individual-specific covariates such as age, education, and length of prison sentence.

Heterogeneous analysis:

We will study heterogeneous effects of the intervention depending on their baseline score of the primary outcome variable. Those who score high on level of plaque have the greatest improvement potential. However, they might also be those with the least interest in taking care of their oral health. As motivational interviewing is designed to also motivate those who are not motivated, they may still experience the greatest improvement from the intervention.

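### The leading test is an unadjusted Mann-Whitney test and no primary analysis is named; adjusting for prison and baseline MPS would raise power from about 70% to 95% (N=320, d=0.286, two-sided, common effect)

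*Combined protocol and SAP*

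**What the plan says.** Statistical model specification gives the test of the overall effect to an unadjusted rank test: "To test the overall effects of the intervention on our primary and secondary outcome variables, we will conduct non-parametric Wilcoxon Mann-Whitney U-tests". The time point of main interest is T1: "our primary interest will be the difference in means at T1, as we expect more missing data at T2".

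The same section then adds several ordinal logistic regressions that include the baseline score. Covariates adds prison dummies, a dummy for the person who delivered the MI conversation, and more: "Covariates that are relevant for such analysis (HASI and depressive symptoms) will also be included in the overall analysis". Neither section says whether the U-test or a regression settles the primary question.

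Randomization is stratified: "We block on prison level, to ensure a balance between treatment and control group in each prison".

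Power calculations contains two separate calculations.

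- The first sizes the U-test "without considering that data is collected at multiple sites": "We choose the non-parametric Wilcoxon-Mann-Whitney test, set alpha to 0.05 and required power to 0.8". It gives 106 prisoners for d=0.5 and 320 for d=0.286. It does not say whether the test is one-sided or two-sided.
- The second gives a minimum detectable effect size (MDES) for four prisons of 100. It assumes that prison explains 20–30% of the outcome variation and that baseline MPS is "expected to explain 50% to 60% of the variation in the post-intervention MPS index score". The result runs from about 0.15 to about 0.55.

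For reading a T2 comparison without a significant difference, Statistical model specification points to the second calculation, "given that power is set to 0.8 and number of sites is set to 4".

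**The concern.** On the plan's own assumptions, prison and baseline MPS together account for 60% (1 − 0.8×0.5) to 72% (1 − 0.7×0.4) of the outcome variation. The U-test leaves all of that as noise. Both variables are already collected and one defines the randomisation blocks, so the loss buys nothing. It matters more here because recruitment is described as very uncertain and attrition as somewhat high.

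Two further consequences follow. If the U-test and the regression disagree, the choice between them would be made after the results are seen. And a reader who takes 0.15 as the detectable effect would read too much into a null U-test.

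**Working it through.** **1. The plan's sample sizes.** Inputs from Power calculations: alpha 0.05, power 0.80, d=0.5 and 0.286. Method: noncentral t for two equal groups, with the Wilcoxon relative efficiency 3/π = 0.955.

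- One-sided: 106 and 320, exactly as stated.
- Two-sided: 134 and 404.

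The stated sizes are therefore one-sided. At N=320 and d=0.286 the U-test has 80.2% power one-sided and 70.3% two-sided. Two-sided 5% is assumed below.

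**2. The plan's MDES.** B is the prison share and R² the baseline share.

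- Fixed prisons: SE = √(4(1−B)(1−R²)/N). With B=0.3, R²=0.6, N=400: SE = √(4×0.7×0.4/400) = 0.0529, MDES 0.149 (stated: 0.15). With B=0.2, R²=0.5: SE = √(4×0.8×0.5/400) = 0.0632, MDES 0.178.
- Random prisons, effect variation 0.05, 3 df: SE = √((0.05 + 4×0.8×0.5/100)/4) = 0.128, MDES 0.547 (stated: 0.55).

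Both ends reproduce. The 0.15 end requires adjustment for prison and baseline. The 0.55 end is driven by random prison effects with 3 df. Neither describes the U-test.

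**3. What the U-test detects at N=400.** MDES ≈ (1.960 + 0.842)/√(400×0.955/4) = 2.802/9.77 = 0.287 (one-sided: 0.255). Power at d=0.15: Φ(0.15×9.77 − 1.96) = Φ(−0.49) ≈ 31%.

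**4. Power with adjustment, N=320, d=0.286.** By formula on a continuous scale with B=0.2 and R²=0.5, the residual share is 0.40 and power is 98%. MPS has only seven levels (2 to 8), so power was simulated on that scale. The settings were four equal prisons, blocks of four, assumed cut-points, d and variance shares on the latent scale, one common effect, and 4,000 trials per setting (simulation error about √(0.7×0.3/4000) = 0.7 points).

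| Prison / baseline share | U-test | Prison-stratified U-test | Rank ANCOVA | Proportional odds |
|---|---|---|---|---|
| 20% / 50% | 70% | 78% | 95% | 96% |
| 30% / 60% | 71% | 82% | 99% | 99% |
| 10% / 30% (below the plan's range) | 70% | 73% | 85% | 87% |

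Two checks at 20%/50% leave the picture unchanged. Half-point scores, under one reading of the two-examiner rule in Other issues, give 67/75/95/95%. Prisons of 100, 100, 100 and 20 give 69/77/94/95%.

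**5. MDES for proportional odds.** At N=400: about 0.195 (20%/50%), 0.17 (30%/60%) and 0.235 (10%/30%). The plan gives no dropout rate. With an assumed 30% loss by T1 (N=280), it is about 0.23 (20%/50%), against 0.34 for the U-test.

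**6. Type I error.** Blocking on prison and then ignoring it makes the U-test conservative. The approximate size is 2(1 − Φ(1.96/√(1−B))): 3.9%, 2.8% and 1.9% for B = 10%, 20% and 30%. Simulated null rates (N=400, 20%/50%, 12,000 trials) were 3.1% for the U-test, 5.3% for the prison-stratified test, 5.5% for rank ANCOVA and 5.9% for proportional odds.

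**The case against.** **Adjustment is already planned.** This is true: the baseline score and prison dummies are in the regressions. The defect is that the unadjusted test holds the overall-effect role and no analysis is named as decisive. The regressions are also not ready to take over as written. HASI is measured at T1, after the intervention. The dummy for the MI provider has no meaning in the control arm, where no MI conversation takes place, so it splits the arm effect.

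**The starting figure of 70% depends on a two-sided test.** This stands. The hypotheses are directional and the stated sample sizes are one-sided. On that basis the U-test starts at 80%, and adjustment for both terms takes it to about 99% by the continuous-scale formula. The gap between 70% and 80% is due to sidedness; only the gap to the adjusted methods is due to not adjusting.

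**The power figures assume the same effect in every prison.** This also stands, and must be said beside them. The plan allows effect variation of up to 0.05 and calls its MDES very sensitive to it. With random prison effects (3 df, N=320, residual share 0.40), adjusted power is 76%, 61% and 33% at variation 0, 0.01 and 0.05. With a zero mean effect and variation 0.05, proportional odds rejected in 26% of simulated trials and the U-test in 13%. So neither test supports inference to prisons in general. But the plan uses prison dummies and includes all four prisons in the county; for inference about those four, the adjusted model is sound.

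**The U-test is valid, and 0.15 is labelled as optimistic.** Both are fair. A significant U-test can be believed. The pointer to the four-site calculation concerns T2, already warns of low power, and 0.287 lies within the quoted 0.15–0.55. The risk of over-reading is the smaller part of this point.

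**Conclusion.** The concern holds. It is a loss of efficiency and an undecided primary analysis, not a bias. At N=320 and d=0.286, two-sided, power rises from about 70% to 95% at the plan's lower variance shares, to 99% at its upper shares, and to 85–87% at shares well below its range. The direction is secure. The exact figure rests on the plan's uncertain variance shares, assumed cut-points for MPS, 320 prisoners analysed at T1, and a common effect across the four prisons. The slightly raised size of the adjusted tests explains only a small part of the gain. The plan should be changed on this point, though a significant result from it as written would stand.

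**What to change.** Name one primary analysis, for example:

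> MPS at T1 is compared between arms by proportional-odds regression on arm, baseline MPS and prison at randomisation, two-sided 5%.

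Rank ANCOVA on the same terms is a reasonable alternative, with simulated size slightly closer to 5%. In addition:

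- Leave HASI and the MI-provider dummy out of this model.
- Keep a prison-stratified (van Elteren) Mann-Whitney test as supportive.
- Treat secondary outcomes the same way, each with its own baseline value where one exists.
- Say that inference is about these four prisons.
- Restate the MDES for the chosen model by simulation on the ordinal scale, at the number expected at T1.

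If the U-test stays primary, state its sidedness and an MDES of about 0.29 at N=400 (two-sided), and do not use 0.15 to interpret it.

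The cost is a few sentences and a short simulation, with no new data. The plan says it was written before any analysis; the change should likewise be dated before any comparison by arm is seen. The downsides are a stated MDES less favourable than 0.15, reliance on proportional odds, and a simulated size of 5.9% (5.5% for rank ANCOVA). The model is a reduced form of the planned regressions, so it does change the text.

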We expect that there will be somewhat high attrition of reasons independent of the intervention. The major reason for attrition is that the prisoner is released from prison sometime between T0 and T1 or between T1 and T2. We do not have capacity or legal rights to follow the prisoner outside of prison, and even if we did it would be hard to get the newly released prisoners to prioritize a follow-up oral examination and questionnaire outside of prison. Another potential reason for attrition is that the prisoner is transferred to a prison outside of Rogaland County. We do not have the capacity to follow a prisoner outside of Rogaland County. However, we do follow-up oral examination and questionnaire on prisoners who are transferred within prisons in Rogaland County.

As participation is voluntarily, prisoners can withdraw their consent, or choose not to show up for T1 and T2. This is a common problem for most RCTs in social science. As subjects in our population is serving time in prison, they have limited alternative activities to engage in, which is likely to somewhat reduce the number of prisoners who choose not to show up at T1 and T2 (except for reasons explained above).

Expected timeline

Data collection started in November 2021 and is likely to continue until the beginning of 2023. We have funding to collect data one day a week for one year in each prison. In the event that we are unable to recruit enough prisoners one of the prisons, resources can be reallocated to one of the other prisons. We have applied for additional funding to extend data collection for an additional two to three months.

We are estimating to recruit around 500 prisoners to the study, based on the capacity we have available in the project. However, the pandemic and access to prisoners makes this estimate very uncertain.

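### The detectable effects of 0.15 to 0.55 and the sample sizes of 106 and 320 hold for prisoners with an outcome, but the plan ties the effects to prisoners recruited and makes no allowance for loss before T1 or T2

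*Combined protocol and SAP*

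**What the plan says.** The Power calculations section has two parts.

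- **Simple two-group comparison, ignoring sites.** "We choose the non-parametric Wilcoxon-Mann-Whitney test", with alpha 0.05 and power 0.8. At an effect size of 0.5, "our required sample size is 106 prisoners". At "the lowest effect size observed in the studies referred to above (0.286), the required sample size is 320".
- **Four-site blocked design.** "We set alpha to 0.05 and required power to 0.8", with four sites, effect size variation of 0 to 0.05, blocking explaining 20% to 30% of variance and baseline MPS explaining 50% to 60%. The result is tied to recruitment: "assuming we can recruit 100 prisoners in each prison, the most optimistic scenario allows us to detect an effect size of about 0.15". The unfavourable end is about 0.55.

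Neither part mentions a loss rate. Elsewhere the plan expects loss. Withdrawal criteria says "We expect that there will be somewhat high attrition of reasons independent of the intervention" and rules out follow-up after release. Expected timeline and Other issues expect further loss during lockdowns. Statistical model specification makes T1 the primary interest because more data will be missing at T2. It warns that a T2 null may be fade-out or low power, and points to the power analysis, "in which we show effect sizes possible to detect at different number of observations", at power 0.8 and four sites.

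**The concern.** A detectable effect depends on the number of prisoners with an outcome at the visit tested. The plan attaches its figures to the number recruited, and expects the two numbers to differ at T1 and to differ more at T2. If the figures contain no allowance for loss, the sensitivity the plan quotes is not what that recruitment delivers at either follow-up visit.

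The cross-reference adds to this. The plan wants to use detectable effects by number of observations to judge a T2 null. If the power section does not contain them, there is nothing to judge that null against.

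**Working it through.** **Inputs.** From Power calculations: alpha 0.05, power 0.8, J = 4 sites, n = 100 per site, effect size variation (ESV) 0 to 0.05, blocking share B 0.20 to 0.30, baseline R² 0.50 to 0.60, and effect sizes 0.5 and 0.286. From Randomization: 1:1 allocation. The documents do not state sidedness, so it is inferred from which version reproduces. They give no retention rate, so 80%, 60% and 40% are assumptions, applied equally to each prison.

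**Step 1. Reproduce 0.15 and 0.55.** For a blocked person-randomised design,

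SE = √{[ESV + 4(1 − R²)(1 − B)/n] / J},

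with J(n − 2) degrees of freedom if ESV = 0 and J − 1 if ESV > 0. The detectable effect is SE times the noncentral multiplier for two-sided 0.05 and power 0.8.

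- Best case (ESV 0, B 0.30, R² 0.60): SE = √(4 × 0.40 × 0.70 / 400) = 0.0529. The multiplier at 392 df is 2.808, giving **0.149**.
- Worst case (ESV 0.05, B 0.20, R² 0.50): SE = √[(0.05 + 4 × 0.50 × 0.80 / 100) / 4] = 0.1285. The multiplier at 3 df is 4.256, giving **0.547**.

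Both match the plan with 100 per prison analysed. One-sided gives 0.132 and 0.424, which do not match. The match is not exact to the last prisoner: 93 per prison gives 0.154 and 0.552, which round to the same figures.

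**Step 2. Reproduce 106 and 320.** Two-group noncentral t, with the sample size scaled by the Wilcoxon asymptotic relative efficiency of 3/π:

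| Effect size | One-sided N | Two-sided N | Plan |
|---|---|---|---|
| 0.5 | 106 | 134 | 106 |
| 0.286 | 320 | 404 | 320 |

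The plan's numbers are recovered exactly on a one-sided basis with no inflation for loss. So the two parts of the power section use different sidedness, and neither says which.

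**Step 3. Blocked design, number observed varied.**

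| Assumed share observed | Per prison | Best case | Worst case |
|---|---|---|---|
| 100% | 100 | 0.149 | 0.547 |
| 80% | 80 | 0.166 | 0.563 |
| 60% | 60 | 0.192 | 0.589 |
| 40% | 40 | 0.236 | 0.638 |

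At 60% observed the best case is 0.192/0.149 = 1.29 times the stated value, and the worst case 0.589/0.547 = 1.08 times.

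**Step 4. Planned Wilcoxon test, unadjusted and ignoring sites, power 0.8.**

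| Total observed | Two-sided | One-sided |
|---|---|---|
| 400 | 0.287 | 0.255 |
| 320 | 0.322 | 0.285 |
| 240 | 0.372 | 0.329 |
| 160 | 0.456 | 0.404 |

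At the same number observed, the two-sided Wilcoxon figure is about twice the blocked best case: 0.287 against 0.149 at 400, and 0.372 against 0.192 at 240.

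**Step 5. Loss that recruitment can absorb.** To keep 320 with an outcome, 500 randomised tolerates 1 − 320/500 = 36% loss, and 400 tolerates 20%. On the two-sided requirement of 404, 500 tolerates 1 − 404/500 = 19%.

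**Step 6. The cross-reference.** The supplied Power calculations text varies ESV, B and R² at one n. The 106 and 320 pair two effect sizes with two sample sizes, but that calculation ignores sites, so it is not the four-site display described.

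**The case against.** **The display may exist.** The cross-reference reads like a description of a plotted curve, and figures are stripped from the supplied text. There is no missing-figure marker in Power calculations, but the flow-chart heading also has nothing beneath it and no marker. This stands: a reader might infer that the plan cites something it never produced, and the documents do not settle that.

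**An effect of 0.15 may still be reachable at T1.** The plan aims for about 500 and expects more than 100 recruits in three of the four prisons. If all 500 were randomised, 20% loss would leave 400. The language exclusion and the 18-room prison count against this, but with no retention rate given, the claim that 0.15 is unattainable is unproven. Equally, the plan never presents the gap between 400 and 500 as an attrition allowance.

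**The worst case hardly moves.** It is dominated by effect size variation on 3 df. Even at 50% observed it reaches only 0.609. This stands.

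**The plan already concedes the point.** It makes T1 primary, and says drop-out raises the detectable effect and that a T2 null is ambiguous. This is true in words, but no figures follow in the supplied text. Other issues says only that imputation or maximum likelihood will be considered, which does not supply them.

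**Extra rows from the blocked model alone would mislead.** The overall T2 comparison uses the unadjusted Wilcoxon test, so best-case blocked rows would flatter it by about a factor of two. This stands and shapes the fix.

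**Conclusion.** The concern holds as one of labelling and omission. The plan's calculations reproduce, so a reader should not infer an arithmetic error. What is wrong is that 0.15 and 0.55 are attached to recruitment, although they require about 100 prisoners per prison with an outcome, and that 106 and 320 are numbers analysed with no allowance for the attrition the plan itself expects.

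The effect on the blocked-model figures is moderate at the favourable end (0.149 to 0.192 at 60% observed, 0.236 at 40%) and small at the unfavourable end (0.547 to 0.589 and 0.638). It matters more for the planned Wilcoxon test, whose two-sided detectable effect is already 0.287 at 400 observed and passes 0.37 at 240.

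These results assume equal loss in each prison, equal prison sizes, the plan's own R² range carried to both visits, and retention values that are not in the documents. Whether the T2 cross-reference is empty cannot be decided from the supplied text. It needs checking.

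**What to change.** Keep the sample size and the analyses.

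1. In Power calculations, label 106, 320, 0.15 and 0.55 as figures for prisoners with an outcome at the visit tested.
2. State the sidedness of each calculation. If two-sided testing is intended throughout, 106 and 320 become 134 and 404.
3. Add one small table of detectable effects at plausible observed numbers for T1 and T2, with separate rows for the baseline-adjusted blocked model and the unadjusted Wilcoxon test. The tables above can serve, with the retention values marked as assumptions.
4. In Statistical model specification, check the cross-reference and point it to that table. Say that a T2 Wilcoxon null will be read against the Wilcoxon row for the number actually observed, not against the blocked-model best case.

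The cost is the table, a few sentences and a less favourable stated sensitivity. No further prisoners are needed.
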